3.1.2 Management plan

The clinical trial will start in September 2017, and will last for 12 months.

This clinical study will be carried out coherently with the Guideline for Good Clinical Practice (GGCP) (CPMP/ICH/135/95) and the current Spanish legislation (RD 1090/2015).

An exhaustive study of the risks and possible inconveniences has been carried out, taking into account that participants' rights, safety and wellbeing prevail over the science. After this analysis, it has been reached the conclusion that the experiment is clearly more beneficial than inconvenient for the subjects that will participate.

The clinical researcher will be responsible of supervising and monitoring the clinical experiment, guaranteeing that it is developed, archived and published according to the protocol defined in the aforementioned normative and legislation. The following activities will be carried out:

- a) Verify that the rights and wellbeing of the participants are constantly protected.
- b) Check that the data obtained during the clinical study are accurate, complete and verifiable.
- c) Guarantee that the experiment is being developed according to the defined clinical protocol, its amendments and prevailing normative and legislation.

It is necessary to highlight the points below:

- d) The clinical study will be only carried out with the pertinent approval of Clinical Ethics Committee (CEC).
- e) All participants must have freely signed the informed consent prior to participating (potential participants will not be coerced; also, an adapted language will be used for doubts solving). In case the informed consent is modified, a new approval from the CEC will be necessary.
- f) In case the informed consent needs to be signed by a legal guardian, the actual participant will be also informed.
- g) A qualified healthcare professional will be responsible for the medical care received by the participants and clinical decisions taken.
- h) The scientific team will be only composed by qualified and experienced personnel.
- i) All the information produced during the clinical study will be registered, handled and archived in such a way that it is possible to communicate, interpret and verify in an accurate way.
- j) Any modification in the electronic Case Report Form (eCRF) will be dated and explained without hiding the original data.
- k) All documentation produced during the trial will be available at all time to the Clinical Research Assistant (CRA), auditor and CEC.
- Confidentiality and privacy will be protected at all time. Spanish prevailing law will apply (LOPD 15/1999).
- m) The clinical trial protocol has been designed to guarantee the quality of the experiment to be carried out.
- n) Neither severe deviations nor protocol modifications will be made without the permission of the sponsor and the pertinent approval of the CEC. A severe modification is that one that may affect:
- o) The safety and physical integrity of the participants.
- p) The scientific validity of the study.

- q) The principal investigator will provide the CEC with a finalization report at the end of the study. If the CEC requires one or more mid-term reports, they will be also provided.
- r) Any adverse event will be communicated to the CEC.
- s) It the clinical study ends earlier than expected or it is cancelled for any reason, the principal investigator will consequently inform the participants and the CEC.

It is not possible to have a totally risk free environment. Many decisions involve managing risks according to the project's assessment of what constitutes an acceptable level of risk and its judgments about the costs and benefits of particular courses of action.

Risk management involves establishing an appropriate governance infrastructure and culture and applying logical and sympathetic methods for establishing the context, identification, analysis, treatment, monitoring and communication of risks.

Table 4 the risk action plan for the current clinical trial. The main objectives are:

- To ensure that the major risks faced by the project are identified, understood and appropriately managed.
- To ensure that the planning and management processes focus on areas where risk management is needed.
- To create an environment where the consortium staff take responsibility for identifying and managing risk.

Risk	Description	Likelihood	Threat	Strategy
1	Not achieving of the challenging scientific objectives	Rare	Major	This risk will be minimized by assessing continuously the project progress and at specific decision points deciding on potential fall-back strategies. At each point, a decision has to be made whether the applied approach will guarantee the achievements of the final targets or not. If not, a fall-back strategy will be applied
2	Delay in starting the study	Possible	Significant	In case the start of the study is postponed, an extension of the study lifetime will be requested
3	The FriWalk breaks down during the development of the trial	Unlikely	Significant	There will be a minimum of 2 FriWalks in the clinical dependencies during the clinical study. If one breaks down, the local technical team will try to fix it with remote support from the walker developers; in case it is not possible, and depending on the actual damage, technology specialist will come to the site to restore the walker into operation.
4	A patient gets injured while using FriWalk	Unlikely	Major	Although it is very unlikely, a patient can fall down and get injured while using FriWalk. In that case, as the study will be carried out within Hospital dependencies, the patient will receive immediate clinical assistance. The insurance will economically cover with the expenses.

Table 4. Risk Action Plan.

5	The number of participants is not enough to guarantee strong scientific results	Possible	Major	A weekly estimation of participants recruited will be set. If the number of participants is not achieved, the recruitment activities will be reinforced. If a severe deviation occurs, an extension of the study lifetime will be requested
6	Problems related to the consortium communication during the study	Unlikely	Significant	Potentiate team building among members and increase face to face or teleconference communications when possible. Gather all points of view and intervention of the project coordinator to solve the problem in case it is needed
7	Problems in the management of the project	Possible	Significant	A close follow up of project activities will be carried out. Periodic meetings and reports are scheduled
8	Problems in the dissemination of results	Possible	Significant	The dissemination activities will be planned from the onset of the clinical study. Periodic reviews are scheduled

3.1.3 Data Management plan

3.1.3.1 eCRF

The eCRF will be designed to store every data obtained by the researchers. One eCRF will be created per participant, by complying the national data protection law. Any clarification, correction or change made in the eCRF will be performed by the sponsor or its representative. The clinical researcher will be responsible of fulfilling correctly the eCRF according to the protocol requirements.

The eCRF will comprise the information contained in Table 5.

Test/questionnaire	Short description
Demographic	Information related to participants' age, gender, technology literacy, etc. will be collected
Consumption of healthcare resources	The consumption of healthcare resources after the intervention will be explored.
Barthel index	Index that evaluates the basic daily activities. It comprises a series of questions. The final result ranges from 0 to 100.
Lawton & Brody index	Index that evaluates the instrumental daily activities. It comprises a series of questions. The final result ranges from 0 to 8.
Short Physical Performance Battery	This test evaluates the physical performance throughout 3 specific tests: balance (both feet, semi-tandem and tandem), gait speed in 4 meters and standing-up from a chair. Time used in completing each activity is evaluated. This test ranges from 0 to 12.
Gait speed	For this test, the patient has to walk 6 m at normal speed. Time is evaluated.
Confusion Assessment Method	This test is administered to evaluate delirium by means of a set of Yes/No questions.
Minimental State Examination	This test evaluates the cognitive performance of the patient by analysing the answers provided to a series of questions. Final score ranges from 0 to 30.
Clock Drawing Test	By means of this test, cognitive impairment is explored by analysing motor skills, attention, understanding and numerical

Table 5. Information in the eCRF.

	knowledge. The patient is asked to draw a clock (a circle with the corresponding 12 hours) and indicate a given hour.
Verbal fluency	Semantic fluency is explored by asking the patient to enumerate as many animals as he/she can in 1 minute time. Phonologic fluency is analysed by requiring the patient to say as many names (no proper names) as he/she can starting with letter 'p' in 1 minute time; the test is administered again but this time with letter 'm'. The final score for both semantic and phonologic fluency is the number of valid words the patient was able to say.
Geriatric Depression Test	This test is applied to explore if a given patient is suffering from depression. It consists in a set of 15 to Yes/No questions; a final score higher than 5 points may indicate depression; if it is higher or equal to 10 indicates depression with more accuracy.
EuroQoL-5D	This questionnaire is administered to evaluate the quality of life of the participants. It comprises 5 items: mobility, personal care, daily activities, pain and anxiety/depression.
Analogue Visual Scale for pain	This scale allows measuring intensity of pain. It consists on a 10cm line in which edges extreme expressions of pain are shown (no pain at all in the left hand-side, the unbearable pain on the right hand-side). Pain intensity is expressed in cm or mm.
Adherence to treatment	To evaluate if patients have committed to the prescribed therapy, a set of questions will be asked.
System Usability Test	This scale is administered to evaluate the usability of the system after being used. The final score ranges from 0 to 100.
Satisfaction	A questionnaire will be applied to evaluate patients' satisfaction after having used FriWalk.
Acceptability	Acceptability of FriWalk will be evaluated throughout a specific questionnaire.

The eCRF service will have, in general, the following functionalities:

- Access control by user roles: clinical researcher, CRA, administrator.
- Real-time verification of consistency in the input data.
- Security guaranteed by SSL-encrypted communications.
- Auditable activity log. All changes will be registered in such a way that the historic value of every field will be maintained. The author, date, time and reason of all changes will be indicated.

The service architecture will be based in a client-server paradigm. The client will consist in the following sections:

- Login: that will allow the start a session by introducing username and password. Depending on the user roles, different options will be available.
- Configuration: only available for the administrator. This section will allow the user to configure technical aspects of the service (URL, etc.).
- Administration: only available for the administrator. Assignation of a participant to a group.
- Form: available for the clinical researcher to upload information related to the development of the study.

The server:

- MySQL database where all the information will be stored.
- REST service.

- Privilege management.
- Data export service.

3.1.3.2 Data collection methods

Data will be collected and uploaded intro de eCRF manually.

3.1.3.3 Data validation

As stated in the general description of the eCRF service, data consistency will be checked for all inputs where verification is feasible (i.e. age of the patient given the date of birth).

3.1.3.4 Security aspects

To protect security and privacy all connections between client and server will be encrypted using SSL protocol.

Besides, only granted researchers will have access to the collected clinical information that will be anonymized prior to being uploaded. Access to information will be managed by the server by means of user privileges.

To avoid issues related to privacy, data will be treated in such a way that it will be impossible to identify the individual patient who owns them.

3.1.4 Plan for statistical analysis

Data will be analysed using statistical information management software. Statistical descriptors will be gathered with a confidence interval of 95%. Tests' results obtained will be analysed considering primary and secondary objectives as well as research hypothesis. The statistical significance level will be established in 0.05. The feasibility of each scale employed will be tested taking into account patients' observations and number of excluded cases due to value loss. The percentage of participants with maximum and minimum theoretical levels will be calculated to estimate range of each scale.

3.2 Social trial

3.2.1 Potential intersection of clinical and social

People who are in the process of recovery, after having left the hospital, benefit from social support (Chronister et al. 2008; Mutran et al. 1995). This social support can be especially effective when those who are in the group have experienced the same problem (Reblin and Uchino 2008; Ussher et al. 2006; Woodgate, Brawley, and Shields 2007) and are thus in a position to encourage one another, model recovery for one another, and provide advice for one another. While the cited studies do not refer directly to rehabilitation after falls, the mechanisms by which peer support groups differ from other forms of support (information, acceptance, and sense of community) seem plausible mechanisms by which a falls-rehabilitation support group might benefit members. The ACANTO system can offer a means of facilitating such contact between users after leaving the hospital. Because the system records details about the mobility state of the user, it can use this to match participants based on similar characteristics. The social network can then convey recommendations to the users about others that they can meet with. Venues for meeting can be proposed that host FriWalk devices where users can meet together and obtain the social support they need by meeting other similar users, and obtain the physical support they need to navigate the venue that they visit.

For practical reasons, we will not test this intersection of clinical and social uses. There are several reasons for this: (1) The clinical testing of the FriWalk will be conducted in Spain, and UNAN do not have sufficient

Spanish language skills to work effectively with that population. (2) Even if testing was conducted in Spain, it would require an additional sample separate from those currently associated with the clinical testing in order to avoid conflating the effects of the two interventions. (3) If testing were conducted in the UK, the extensive preparation and delay in gaining ethical approval to work with a clinical population (via the NHS) renders the task infeasible. For these and other reasons, we decided not to explore the "bridging" scenario, even though it holds strong potential on theoretical grounds. Nevertheless, we believe that if we test the social scenario and demonstrate its effectiveness, the joint findings of both the clinical intervention and the social intervention will show that the middle ground, the intersection between the two, is an effective and plausible way of combining the benefits of the ACANTO system. Thus, not testing the intersectional scenario is not an exclusion of an important test, but testing the system at the two ends of the spectrum (the clinical and social ends) shows that if both ends of the spectrum are successful, the intersection can be assumed to some extent.

3.2.2 A social intervention

The social intervention will therefore focus on the social use of the walker in a non-clinical setting. As mentioned previously, there are two components: the FriWalk and the social network. The social network is the means by which the recommender system provides recommendations to users. The FriWalk provides the means of providing physical support for users, as well as providing an enhanced experience for the user. In the social intervention, we aim to test both components of the system. Both components are expected to have benefits on the users and testing of both components can be associated with measurable outcomes. In the sections below, we outline the specific objectives, measures and design of studies to test the system.

3.2.3 Design of the trial protocol

Firstly, a brief summary of the intervention will be helpful. There are two strands of the intervention: (1) testing of the social network and recommender system, and (2) testing of the FriWalk in a social context.

Testing the social network and recommendation system

The first part of the intervention, testing the social network and recommendation system, will involve recruiting a group of older adults to use the FriTab which contains the CPSN API installed. The CPSN will be populated with various events and participants will be asked to rate the quality of the recommendations. There will also be an event organised by the experimenters via the system to test how well it brings together people who have similar interests. We will test whether participants who use the social network and engage in the recommended activities are consequently more socially and physically active as a result of taking part (longitudinal comparison) and compared to a control group who do not take part (between-groups comparison).

Testing the FriWalk

The second part of the intervention will involve testing the FriWalk. To do this, an experimenter will set up a group activity via CPSN API for the FriTab (visiting the museum) to which numerous participants will be invited. Participants will receive a guided tour of the museum with the assistance of the FriWalk and the activity will be repeated on several occasions. We expect that this experience of using the FriWalk will reduce fear of falling while at the museum, will enhance the experience of visiting the museum, and will encourage bonding between the participants. These effects will be stronger for those using the FriWalk compared to those who (a) do not use the FriWalk in the museum, and (b) who do not attend the event.

3.2.3.1 Objectives

Broadly speaking, there are two objectives for both the CPSN and the FriWalk. The use of both should increase both (1) *social involvement* and (2) *physical activity*. There are several other objectives listed below, and the two key objectives are broken down into more detail below.

Controlled factors

While there are clear objectives around what we want the system to achieve, these will be affected by several interacting variables such as the user's perception of the system's ease-of-use, their enjoyment of the system and their sense of the usefulness of the system. These variables are drawn from the Unified Theory of Acceptance and Use of Technology (UTAUT) (Morris, Hall, Davis, Davis, & Walton, 2003) and we expect that a user's perception of the system's ease-of-use (for example) will affect the benefits that they gain from using it; if they find it hard to use they are less likely to adopt recommendations or find it helpful. These control variables apply both to the FriTab API and to the FriWalk (i.e. two sets of questions). While we treat them as control variables, we also expect to see some changes in the levels of enjoyment and sense of usefulness. Increasing use should, hopefully, increase these levels. The variables we will measure are:

- 1. Performance expectancy Perception of the extent to which the system will be/is useful.
- 2. Effort expectancy Perception of the extent to which the system will be/is easy to use.
- 3. Attitude towards the system positive or negative view of the system.
- 4. Social influence Perception of the extent to which other people like or dislike the system.
- Facilitating conditions Perception of the extent to which someone helps in getting used to the system.
- 6. Self-efficacy Perception of the extent to which the user can use the system by themselves (aided or unaided).
- Anxiety Perception of the extent to which the system makes one feel anxious when using it (e.g. fear of making mistakes).
- Intention to use the system The extent to which the user says they would use the system again.
 This is a clear outcome measure that expresses overall intention to use the system.

Outcome measures (social network)

There are several general objectives and accompanying specific objectives.

Firstly, for the testing of the *CPSN*:

- 1. Social involvement
 - a. Perceived social involvement: this should increase as a result of using the system, but will interact with the user's extent of use of the system. The more they use it, the more

benefits they will receive. Those who do not engage much with the system are not expected to show benefits.

- b. Actual social involvement: by using participant diaries, we will show the effect of using the social network on actual involvement.
- c. Quality of recommendations: the more that a user discloses to the system, the greater the quality of the recommendations.
- d. Turnout to event: users who are more engaged with the system and who perceived higher quality of recommendations will be more likely to attend an event to which they are invited. This event will be organised by the experimenters and numerous people will be invited.
- e. Liking of the participants: At the event, liking for each other will be greater depending on the number of similar interests as recorded by the system compared to groups whose members have been randomly selected (similarity-attraction hypothesis; Byrne, 1972).
- 2. Physical activity
 - a. Number of steps taken: as a result of being more socially involved and attending an event, participants should show an increased number of steps compared to their own pattern of activities in a similar period without the intervention. They will also show more steps compared to a control group who do not take part in the intervention.
- 3. General well-being
 - a. Well-being: as a result of having more physical activity, users should show increased levels of subjective well-being (Netz et al. 2005).
 - b. Perceived sleep quality: this should increase as a result of having more physical activity. We know that sleep quality is affected by physical activity (King et al. 1997; Sherrill, Kotchou, and Quan 1998) and that sleep is linked to poor health outcomes (Strine and Chapman 2005). Therefore, it is an important finding if physical activity can increase sleep quality through use of the ACANTO system.

Outcome measures (FriWalk)

Then for the testing of the *FriWalk*. We intend to organise several events where users will come to a museum to test the FriWalk devices. It will involve an administrator/experimenter setting up an event and inviting users to come to the event. Users may be selected based on their stated interests (e.g. history) and may be matched based on their performance abilities (e.g. speed of walking). The experimenter will collaborate with a museum to arrange the event. UNAN has numerous museums that may be available for collaboration (e.g. Centre for Life, The Great North Museum, the Discovery Museum, or Segedunum Roman Fort).

The outcome measures are:

- 1. Physical activity
 - a. Step count: there should be an increased number of steps as a result of taking part in the activity
- 2. Psychological confidence
 - a. Fear of falling: Reduced fear of falling when using the device. This will be measured at baseline (T 1.2.4 questionnaires).

- b. Less anxiety about going out to attend an event where the FriWalk will be used
- 3. Social and emotional bonding
 - a. Sense of common identity: Social bonding/sense of shared identity as "FriWalk user group"
 - b. Increased perceived wellbeing as a result of shared identity (C. Haslam, Cruwys, and Haslam 2014; S. A. Haslam et al. 2009)
- 4. Improved ability to use the museum
 - a. Time taken to find facilities: it should be quicker for users who are unfamiliar with the environment to find facilities when they have the FriWalk.
- 5. Improved sleep quality
 - a. Subjective sleep quality: this should increase as a result of increase physical activity (see above (3b) for the rationale).

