Test event	To test the system, the experimenters will run an interactive workshop and will advertise it via the ACANTO social network. The topic of this workshop is to be decided, but it may be something like, "A guide to smartphones for the older user." The activity will be tagged with relevant tags (e.g. "technology", "internet") and users who express these interests should receive a recommendation for the workshop. Turnout will be monitored at the event and liking for others in the group will be assessed.	
Return and debrief	After the 2 weeks, all participants will return and be debriefed on the purpose of the study. Additional measures will be taken via a short questionnaire (to see changes from the questionnaire administered at the start of the study).	

Table 10. Phases of FriWalk study

	Phase 1: Ethics, recruitment and collaboration
Ethics	Ensure ethical approval is obtained from UNAN ethics procedure
Recruitment	Recruit interested participants to take part in the FriWalk trial.
Collaboration	Collaboration with museums to implement FriWalk devices in the environment.
	Phase 2: Pilot testing
Testing at UNAN	Devices will be set up on UNAN premises and participants will be invited to try out the devices. Data will be collected about users' average walking pace to assist with matching participants for the museum trial.
Baseline tracking	Participants will be given diaries and step counters to monitor their baseline activity.
	Phase 3: Museum testing
Museum tour start	 Participants will be invited to a tour of a museum where they will be given a FriWalk. Approximately 4 participants will be in each group, assuming that 4 FriWalk devices will be available. Each group will be tested on separate days. Some of these events may be advertised via the social network system. Participants may be matched based on their average walking pace or ability.

Pre-tour questionnaire	Questionnaires will be completed before the tour.
Tour	The tour will involve a programmed route during which the FriWalk will guide the user around the museum. An experimenter will accompany the participants.
Post-tour questionnaire	After the tour, a questionnaire will be completed to ask about the experience.
Control group	A tour will be arranged without the FriWalk and will act as a control group. Questionnaires will be completed before and after.
Second control group	Participants in the no-tour, no-FriWalk group will attend the university to provide answers to a questionnaire.

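### Interest selection and pace matching are described only for the FriWalk museum tours, so if they are used there alone, a bonding difference from the comparison tour could partly reflect who was invited

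*Protocol*

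**What the plan says.** **FriWalk events.** Section 3.2.3.1, under the FriWalk outcome measures, introduces the museum events: "We intend to organise several events where users will come to a museum to test the FriWalk devices". It then allows selection and matching of those invited: "Users may be selected based on their stated interests (e.g. history) and may be matched based on their performance abilities (e.g. speed of walking".

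**Table 10, FriWalk tour (section 3.2.3.4).** The row on the start of the museum tour concerns participants who receive a FriWalk, in groups of about four. It adds: "Participants may be matched based on their average walking pace or ability". It also allows some of these events to be publicised through the social network. It does not mention selection on interests.

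**Table 10, pilot testing.** "Data will be collected about users' average walking pace to assist with matching participants for the museum trial". The tours meant are not named.

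**Table 10, comparison tour.** "A tour will be arranged without the FriWalk and will act as a control group". Questionnaires before and after are the only other detail. The recruitment list gives 10 participants for each tour and 10 for a group with no tour, without saying how people are allocated.

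**Outcome.** Section 3.2.3 expects that using the FriWalk "will encourage bonding between the participants", and more so than on a visit without the device. Section 3.2.3.1 lists the outcome as "Sense of common identity: Social bonding/sense of shared identity as" a FriWalk user group, and next to it a gain in well-being that it attributes to shared identity. Table 8 measures common identity with two items on unity within groups.

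**Similarity.** Outcome 1e of the social network study predicts that "liking for each other will be greater depending on the number of similar interests as recorded by the system", relative to groups chosen at random.

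**The concern.** The comparison of the two tours is meant to show what the device adds. That reading needs the tours to differ in the device and not in how their members were chosen. As written, a team could invite people with a common interest to the FriWalk tours, and fill the comparison tour with whoever was available, without departing from the protocol.

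This matters for bonding in particular, because the protocol's own hypothesis in the sister study is that shared interests make people like each other more. A higher unity score on the FriWalk tours would then have two explanations, and the well-being result tied to shared identity would inherit the same ambiguity. Section 3.2.6 plans ANOVA between experimental and control groups and does not name shared interests or pace matching as factors to control. The no-tour group cannot separate the explanations, because its members take part in no tour group.

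**Working it through.** The protocol gives no figure to reproduce here. The check has two parts: comparing what is stated for each tour, and an illustration of size.

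**1. What is stated for each tour**

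| Step | FriWalk tour | Tour without FriWalk |
|---|---|---|
| Selection on stated interests | Permitted (section 3.2.3.1 only) | Not mentioned |
| Matching on pace or ability | Permitted (section 3.2.3.1 and Table 10) | Not mentioned; the pilot-testing sentence might cover it |
| Publicity through the social network | Permitted for some events (Table 10) | Not mentioned |
| Group size | About 4 | Not mentioned |
| Allocation of people to the tour | Not described | Not described |

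The two halves of the concern have unequal support.

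- *Interests.* The permission is tied to events held to test the devices, and outcome 1e links shared interests to liking. The step from liking to unity or shared identity is a close inference, but an inference.
- *Pace.* The explicit matching statements sit with the FriWalk tours. Nothing in outcome 1e concerns walking pace, so the protocol supplies no reason to expect pace matching to raise bonding. It is only a possible imbalance between the tours.

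**2. Illustration of size**

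Inputs:

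- n = 10 per tour, from the recruitment list in section 3.2.3.4.
- Two-sided level 0.05. This is an assumption: section 3.1.4 states 0.05 for the clinical trial, and section 3.2.6 gives no level for the social trial.
- True device effect zero.
- Shift d in the bonding score from composition alone, in SD units. This is an assumption; the protocol gives no value.

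The calculation is a two-sample t test, a simplification of the planned ANOVA, and it ignores dependence between people on the same tour.

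Degrees of freedom = 2 × 10 − 2 = 18, so the critical value is 2.101. Noncentrality = d × √(n/2) = d × √5 = 2.236 d. The probability of a positive result is that of a noncentral t variable falling beyond ±2.101.

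| d (assumed) | Noncentrality | P(positive result), no device effect |
|---|---|---|
| 0 | 0 | 5.0% |
| 0.2 | 0.447 | 7.1% |
| 0.3 | 0.671 | 9.7% |
| 0.5 | 1.118 | 18.5% |
| 0.8 | 1.789 | 39.5% |
| 1.0 | 2.236 | 56.2% |

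Whatever d is, the estimated difference between tours is off by d. If both tours follow one rule, d from this source is zero in expectation and the rate returns to 5.0%, again ignoring dependence within tours.

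**The case against.** The strongest reply is that the asymmetry is inferred from silence. Both source sentences are permissive, and nothing says the comparison tour will be composed differently. The pilot-testing sentence speaks of matching for the museum trial as a whole, and the museum phase of Table 10 contains both tours. It could therefore cover both arms, or even mean matching across arms, which would reduce imbalance. This stands in part: the scope is ambiguous, although the pace data come from a session in which people try the device and no text extends matching to the comparison tour. A reader might infer that the protocol prescribes composed FriWalk groups against uncomposed controls; it does not. It permits that and contains nothing to prevent it.

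Second, outcome 1e belongs to a different event, names liking and concerns interests. This stands. A reader might infer that the protocol itself predicts more bonding from pace matching; it does not. Inviting people with an interest in history to a museum may also be no more than an invitation filter.

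Third, a reader might infer that randomisation could not help. That is too strong. If interest selection is applied to one pool before people are randomised to the tours, it is balanced in expectation. The problem would remain only if selection or group forming then differed by tour.

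Fourth, the illustrated percentages follow directly from the assumed shifts and say nothing about which shift is likely. This stands in full.

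**Conclusion.** The point holds in a limited form. The protocol permits interest selection and pace or ability matching for the FriWalk tours, states neither for the comparison tour, and is unclear on whether matching covers both. If interest selection is used for FriWalk tours only, differences between the tours in bonding or shared identity, and in the well-being attributed to it, could partly reflect who was invited. For pace matching the documents support only a possible imbalance, with no stated link to liking.

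The size is unknown. The rates of 9.7%, 18.5% and 39.5% at assumed shifts of 0.3, 0.5 and 0.8 SD show how a composition effect would appear at 10 v 10 with an assumed two-sided 0.05 level. They should not be read as the expected false-positive rate of this study. The bias is conditional on the permission being used for one tour only, but excluding it is cheap, so the text should be changed.

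**What to change.** Amend both section 3.2.3.1 (FriWalk outcome measures) and Table 10, since changing the table alone would leave the interest-selection sentence standing. State that:

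1. Participants for the FriWalk tour and the tour without it come from one pool, selected by the same interest rule.
2. People are allocated at random from that pool to the two tours.
3. Groups within each tour are formed by the same rule, including the same pace or ability matching.
4. The pace data collected at pilot testing serve both tours.

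Alternatively, drop interest selection and matching for both tours.

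The cost is wording, plus interest and pace data for the 10 comparison-tour participants. Forming groups first and then allocating whole groups is not needed. At about 4 per group it would leave roughly three groups per tour (10/4 = 2.5) and make the group the unit of allocation, a larger change than this problem calls for. If one rule for both tours was always intended, the amendment simply records it.
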